7.10 Clinical Laboratory Evaluations

Clinically relevant deviations of laboratory test results occurring during or at completion of the study must be reported and discussed with Covance personnel. The results should be evaluated for criteria defining an AE and reported as such if the criteria are met. Repeated evaluations are mandatory until normalization of the result(s) or until the change is no longer clinically relevant. In case of doubt, Covance personnel should be contacted.

Safety labs (hematology, clinical chemistry and urinalysis) do not need to be repeated at baseline if the Baseline visit is taking place within 48 hours of the screening labs being collected from an individual subject.

Subjects should be instructed to fast for at least 8 hours prior to scheduled safety lab collections.

Clinically notable laboratory findings are defined in [Appendix 3](#).

Hematology

Hemoglobin, hematocrit, red blood cell (RBC) count, white blood cell (WBC) count with differentials and platelet count will be measured.

Clinical chemistry

Sodium, potassium, creatinine, BUN/urea, uric acid, chloride, albumin, calcium, alkaline phosphatase, total bilirubin, bicarbonate/HCO₃, LDH, GGT, AST, ALT, CK, glucose, total

cholesterol, triglycerides. If the total bilirubin concentration is increased above 1.5 times the upper limit of normal, direct and indirect reacting bilirubin should be differentiated.

Urinalysis

Measurements for specific gravity, protein, glucose and blood will be performed. Microscopy, WBC, RBC and sediments will also be assessed in case of an abnormal test result.

Special clinical laboratory evaluations

Stool samples will be collected to check for occult blood at screening and baseline. Screening fecal samples can be collected at any time during the Screening period, and baseline fecal samples must be collected within 72 hours of Day 1. If fecal screening samples are collected within 72 hours of Day 1, then they do not need to be repeated for the Baseline visit. In the event that a subject is unable to produce a stool sample for sampling, the site medical staff may elect to produce a sample via digital extraction from the rectum.

Details regarding collection methods and processing are outlined in the Central Laboratory Manual.

7.11 Vital Signs, Physical Examination, and Other Safety Evaluations

Vital signs will include the collection of oral body temperature (recorded in °C), blood pressure (BP)–sitting and standing –and pulse measurements. At Screening, for eligibility determination, three sets of systolic and diastolic BP and pulse rate measurements will be collected after the subject has been sitting for 3 minutes, with back supported and both feet placed on the floor and the mean will be used to determine eligibility. A single set of BP and pulse rate measurements will then be collected after three minutes in the standing position.

A single set of sitting BP measurements will be collected at subsequent visits.

Physical exams will include assessment of general appearance, skin, lymph nodes, HEENT, neck, thorax/lungs, cardiovascular, abdomen, musculoskeletal, and neurological systems.

Height in centimeters (cm) and body weight [to the nearest 0.1 kilogram (kg) in indoor clothing, but without shoes] will be measured. Body mass index (BMI) will be calculated using the following formula:

$BMI = \text{Body weight (kg)} / [\text{Height (m)}]^2$. BMI results will be documented in the CRF to 2 decimal places.

7.12 Electrocardiogram (ECG)

The ECGs must be recorded after 10 minutes rest in the supine position to ensure a stable baseline. PR interval, QRS duration, heart rate, RR interval, QT, QT corrected by the Fridericia correction formula (QTcF) will be collected. The QTcF should be used for clinical decision-making. ECGs must be collected, analyzed and appropriately signed and archived at the study site; the site will also store all ECG readings digitally (if possible). For any ECGs with subject safety concerns, duplicate ECGs must be performed to confirm the safety finding. Clinically significant ECG findings at baseline must be discussed with the Sponsor before administration of study treatment. Clinically significant abnormalities must be reported in the AE CRF.

7.13 Pharmacokinetic Analysis

The PK samples will be collected at the timepoints defined in the Assessment schedule (Table 9). Follow instructions outlined in the Central Laboratory Manual regarding sample collection, numbering, processing and shipment. See Section 7.15 regarding the potential use of residual samples.

In order to better define the PK profile, the timing of the PK sample collection may be altered based on emergent data. The number of samples/blood draws and total blood volume collected will not exceed those stated in the Laboratory Manual. Changes to the PK Assessment schedule, if any, will be communicated to the sites in the dose adjustment minutes.

The PK samples will be obtained and evaluated in all subjects at all dose levels. Untreated (placebo) samples will not be analyzed.

Concentrations of plasma total MAA868 (i.e. MAA868 that is bound to FXI or not bound to FXI) will be determined by a validated LC-MS/MS method. A detailed description of the method used to quantify the concentration of total MAA868 will be included in the bioanalytical raw data and in the Bioanalytical Data Report.

All concentrations below the LLOQ or missing data will be labeled as such in the concentration data listings.

For standard PK abbreviations and definitions see the list provided at the beginning of this protocol.

The following PK parameters will be determined, where data permit, using the actual recorded sampling times and non-compartmental method(s) with Phoenix WinNonlin (Version 6.2 or higher): C_0 (the concentration at the end of infusion), AUC_{last} , AUC_{inf} , C_0/D , and AUC/D , based on the plasma concentration data.

The linear trapezoidal rule will be used for AUC calculation. The terminal half-life of MAA868 ($T_{1/2}$), volume of distribution (V_{ss}) and clearance (CL) will also be estimated, if feasible, based on the data.

7.14 Other assessments

7.14.1 Exploratory Biomarker assessments

Biomarkers including, but not limited to, D-Dimer and biomarkers of thrombogenesis and coagulation may also be studied.

The list may be changed or expanded further, as it is recognized that more relevant or novel biomarkers may be discovered during the conduct of the study.

Sample(s) will be collected at the timepoint(s) defined in the Assessment schedule (Table 9).

Follow instructions for sample collection, numbering, processing and shipment provided in the central lab manual. Detailed descriptions of the assays will be included in the Bioanalytical Data Reports.

7.14.2 Immunogenicity (IG)

The IG samples will be collected at the timepoints defined in the Assessment schedule (Table 9).

Follow instructions outlined in the Central Laboratory Manual regarding sample collection, numbering, processing, and shipment. See Section 7.15 regarding the potential use of residual samples.

Immunogenicity analytical method(s)

A ligand-binding assay will be used to detect anti-MAA868 antibodies. The analytical method will be described in detail in the IG Bioanalytical Data Report.

7.15 Use of residual biological samples

Residual blood samples may be used for another protocol specified endpoint.

Any residual samples remaining after the protocol-defined analysis has been performed may be used for additional exploratory analysis. This may include but is not limited to using residual samples for protein binding, metabolite profiling, biomarkers of transporters or metabolic enzyme activity (such as 4-beta-hydroxycholesterol levels) or other bioanalytical purposes (e.g. cross check between different sites and/or stability assessment). Given the exploratory nature of the work, the analytical method used for those assessments may not be validated. As such, the results from this exploratory analysis will not be included in the clinical study report.

8. SAMPLE SIZE AND DATA ANALYSES

8.1. Determination of Sample Size

A sample size of 16 subjects per treatment dose cohort with a ratio of 3:1 for MAA868 and placebo treatment assignment is based on historic data considerations. For example, if the observed proportion of patients in a cohort achieving target levels of inhibition is 11/12, the 90% confidence interval would be 0.66 to 0.996.

8.2. Analysis Populations

All Randomized Set will include all subjects who are randomized

Full Analysis Set will include randomized subjects excluding those subjects who are randomized into the study in error and did not receive study drug. Subjects will be analyzed based on the assigned treatment at the randomization.

Per Protocol Set will include subjects in Full Analysis Set and those subjects have no major protocol deviation after randomization.

Safety Set will include randomized subjects who at least received one dose of study drug. Subjects will be analyzed based on the actual treatment taken.

PK/PD Analysis Set will comprise all subjects who received at least one dose of study drug and have at least one PK/PD assessment. Subjects will be analyzed based on the actual treatment taken.

8.3. General Considerations

All efficacy analysis will be based on the Full Analysis Set or Per Protocol Set and will be performed based on the assigned treatment arm at the randomization. Only descriptive statistics will be summarized, no statistical inference will be calculated in efficacy.

Safety analysis will be performed using Safety Set. Subjects will be analyzed based on the actual treatment taken.

PK and PD analysis will be based on PK/PD Analysis Set.

Continuous variables will be summarized by number of subjects [n], mean, standard deviation [SD], median, minimum [min], and maximum [max]. Categorical variable will be summarized using frequency [N] and percentage [%].

8.4. Demographics and Baseline characteristics

All baseline summaries will be based on the All Randomized Set and Full Analysis Set populations.

Gender, race and ethnicity will be summarized using counts and percentages. Age, height (cm), and weight (kg) will be summarized with descriptive statistics (number of subjects [n], mean, SD, median, minimum [min], and maximum [max]). Age may be summarized by decades using N and %.

The listing of subjects with abnormal physical examination findings at screening will be presented. The number and percent of subjects with medical history events will be summarized. Vital signs

collected at screening (sitting diastolic and systolic blood pressure, pulse, temperature and body weight) will be summarized with descriptive statistics (n, mean, SD, median, min, and max).

8.5. Efficacy Analysis

Primary Efficacy Outcome Measures

Within each treatment cohort patients will be randomized 3:1 to active drug or placebo.

The primary analysis variable is whether a subject will achieve a certain percentage FXI inhibition at trough (Day 91). The response rate per treatment group will be calculated by number of subjects who achieve targeted FXI inhibition rate divided by the total number of subjects in the treatment group. The dose regimens and targeted FXI inhibition achievement for Cohorts 1 and 2 are as follows

Cohort 1 (MAA868 120 mg monthly or placebo): Targeted to achieve $\geq 50\%$ FXI inhibition in 90% of subjects at trough (Day 91).

Cohort 2 (MAA868 180 mg monthly or placebo): Targeted to achieve $\geq 90\%$ FXI inhibition in 90% of subjects at trough (Day 91).

The “on treatment” trough FXI levels will be used for the primary analysis, where “on treatment” FXI level is defined as a value which is collected within 30 (± 5) days after the last administration of MAA868. The estimate of the responder rate (%) at Day 91 will be presented for each dose regimens of MAA868 together with 2-sided 90% confidence intervals (CI) computed via the Clopper-Pearson exact binomial method.

Secondary Efficacy Outcome Measures

The secondary efficacy analysis is to evaluate the proportion of subjects achieving FXI inhibition $\geq 50\%$, $\geq 80\%$, and $\geq 90\%$ at trough after the first and second dose (Day 31 and Day 61) at 3 dose levels of MAA868. The analyses described for the primary endpoint will be repeated for the secondary efficacy variables as follows:

- Cohort 1 (MAA868 120 mg monthly or placebo): at Day 31 and 61.
- Cohort 2 (MAA868 180 mg monthly or placebo): at Day 31 and 61
- Cohort 3 (MAA868 TBD mg monthly or placebo): at Day 31 and 61

8.6. Safety Analysis

The safety evaluation includes the analysis of bleeding events, AEs, major cardiovascular, cerebrovascular, systemic arterial, and venous thromboembolism events, laboratory data, ECG, vital signs, hypersensitivity reactions, injection site reactions, and development of anti-drug antibodies. All safety analysis will be performed using the Safety Set.

Adverse Events

The Investigator’s verbatim term of each AE will be mapped to system organ class (SOC) and preferred term (PT) using the MedDRA dictionary.

Treatment-emergent Adverse Events (TEAEs) will be of primary interest. The TEAEs will be summarized by SOC and PT; a subject will only be counted once per SOC and once per PT within a treatment. If a subject reports more than one AE with the same PT, the AE with the maximum severity will be presented. Subject counts and percentages and event counts will be presented for each treatment and totaled for all treatments for the following summaries:

- All TEAEs
- Serious TEAEs
- All TEAEs by severity
- All TEAEs by relationship to study drug
- TEAEs potentially related to study drug
- TEAEs potentially related to study drug by severity
- TEAEs leading to discontinuation of study drug
- TEAEs leading to withdrawal from the study

Adverse events of special interest (AESI) will be reported for a selection of interested AE terms that are specific to Sponsor's product and program, for which ongoing monitoring and rapid communication by the Investigator to the Sponsor can be appropriate.

The AESIs for this study are defined as follows:

1. TERM 1
2. TERM 2

Similarly, to the TEAE summary, the AESI will be summarized in the following:

1. All AESIs
2. Serious AESIs
3. All AESIs by severity
4. All AESIs by relationship to study drug
5. AESIs leading to discontinuation of study drug
6. AESIs leading to withdrawal from the study

No statistical inference between the treatments will be performed on AEs.

Listings will be presented by subject for all TEAEs, AESIs, as well as for SAEs, TEAEs associated with outcome of death, and TEAEs leading to discontinuation from the study.

Bleeding Events

An analysis will be performed for the composite safety endpoint of major and CRNM bleeding events which occur on-treatment from the first dose of the study drug to the last dose of the study drug + 30 days if the subject permanently discontinues the study drug prior to the third dose on Day 91. The number of events and the incidence of adjudicated bleeding events will be tabulated

based on ISTH definition by treatment including the composite endpoint of major bleeding events and/or CRNM bleedings.

Major bleeding events (Yes/No)

CRNM bleeding events (Yes/No)

Total bleeding events (Yes/No)

If a subject has more than one bleeding event in each above category, the subject will be counted only once in the tabulation.

The adjudicated outcome by the CIAC will be the basis for any interim and final analysis.

Major cardiovascular, cerebrovascular, and venous thromboembolic events

An analysis will be performed for the composite safety endpoint of major cardiovascular, cerebrovascular, and venous thromboembolic events which occur on-treatment from the first dose of the study drug to the last dose of the study drug + 30 days if the subject permanently discontinues the study drug prior to the third dose on Day 91.

The number of events and the incidence of adjudicated events will be tabulated based on the outcomes adjudicated by experienced medical personnel, and the adjudicated outcome will be the basis for any interim and final analysis.

Clinical Laboratory Evaluations

Clinical laboratory results in continuous values at each timepoint and for change from baseline will be displayed using summary statistics (n, mean, median, SD, minimum and maximum values).

A laboratory value that is within the central laboratory's reference range will be considered normal. A laboratory value that is outside the central laboratory's normal range will be considered abnormal and will be flagged as either high (H) or low (L). The number and percentage of subjects with abnormal laboratory values will be summarized for each scheduled visit. In addition, shift tables will be presented to display the shift in the normal range categories (L, normal [N], H) from baseline to specified timepoint. Laboratory results in clinical significance will also be summarized in tabulation.

All clinical laboratory data will be presented in listings. Baseline is defined as the result obtained prior to first administration of study medication. Laboratory data will be summarized in SI units.

Vital Sign Measurements

Pre-dose values, post-dose values, and the change from baseline in vital sign measurements (sitting diastolic and systolic blood pressure, pulse, temperature and body weight) will be summarized with descriptive statistics (n, mean, SD, median, min, and max) at each timepoint by treatment. The baseline value will be value just prior to first administration of study medication.

ECG Parameters

The ECG measures (QTc-F, QT, RR, ventricular rate, PR, and QRS) will be listed and summarized with descriptive statistics (n, mean, SD, median, min, and max) at each timepoint by treatment.

The listings of subjects with abnormal ECG results, as judged by the Investigator, will be displayed and will be calculated. The baseline will be the value just prior to first administration of study medication.

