2.2. Secondary objectives and endpoints

Objective	Endpoint

 To evaluate the proportion of patients achieving FXI inhibition $\geq 50\%$, $\geq 80\%$, and $\geq 90\%$ at trough after the first and second dose (Day 31 and Day 61) at different dose levels of MAA868 	
 Occurrence of achieving $\geq 50\%$, $\geq 80\%$, and $\geq 90\%$ inhibition of FXI ($< 50\%$, $< 20\%$, or $< 10\%$ free FXI) at trough on Day 31 and Day 61 at different dose levels of MAA868

 To evaluate the safety and tolerability following multiple s.c. administration of MAA868 compared to placebo in patients with AF 	
 Occurrence of adverse events (AEs), including serious AEs (SAEs) during the Treatment Period and through EoS

 To evaluate the incidence of major bleeding events, clinically relevant non-major (CRNM) bleeding events and total bleeding with MAA868 relative to placebo during the treatment period 	
 Occurrence of confirmed major bleeding events, CRNM bleeding events and total bleeding events during the treatment period

 To evaluate the immunogenicity of MAA868 compared to placebo. 	
 Screening and confirmation for anti-drug (MAA868) antibodies (ADA)

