3. INVESTIGATION PLAN

3.1. Overall Study Design and Plan Description

This is a phase 2a, randomized, subject- and investigator-blinded, placebo-controlled, multiple ascending dose-ranging study to assess the PK/PD, safety, tolerability, and immunogenicity of MAA868 in patients with AF or flutter.

Patients will be enrolled in at least 2 and up to 3 cohorts of approximately 16 patients each for a total of up to 48 subjects (Figure 1A). Patients in cohort 1 will be randomized 3:1 to receive a 120 mg dose of MAA868 or placebo, respectively on Day 1 with two subsequent monthly injections. After approximately 10 of the patients in cohort 1 have been randomized, a safety review of emerging safety and PK data from cohort 1 will take place. Cohort 2 may be initiated after it is confirmed by the Sponsor’s Medical Monitor and the Covance Lead Project Physician that the cohort 1 dose was safe and well tolerated after at least half of the patients in cohort 1 have been randomized. Likewise, after approximately 10 of the patients in cohort 2 have received their second dose and have been followed for at least an additional 14 days, interim safety, tolerability, and other analyses will be evaluated by the Sponsor. Based on emerging data, the Sponsor may elect to:

[figure not shown]
- Enroll cohort 3 to evaluate a higher, lower, or a previously studied dose of MAA868
- Terminate the study

The study is comprised of 3 periods:

- (1) Screening period of up to 28 days
- (2) Treatment period with MAA868 administered s.c. monthly (or matching placebo) (randomized 3:1) for 90 days
- (3) Follow-up period up to end of study (Day 170).

Following the screening period of up to 28 days, all patients that meet the study eligibility criteria (Section 4.1 and Section 4.2) will have baseline efficacy and safety assessments performed on Day 1 and then randomized to active or placebo (Figure 1B).

Figure 1: Overall study design

The first dose of study drug will be administered at the study center on Day 1. The second and third doses of study drug will also be administered at the study center to patients on the Day 31 visit and Day 61 visit, respectively.

During the treatment period, patients will return to the study center on Day 11, Day 31, Day 41, Day 61, Day 71, and Day 91 for safety assessments such as vital signs, AE assessments, laboratory tests, PK, PD, thrombogenesis biomarkers, and other study assessments according to the assessment schedule shown in [Table 9](#).

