3.2. Discussion of Study Design, Including the Choice of Control Groups

Rationale for route of administration and treatment duration. The s.c. route of administration was chosen because it is the route of administration anticipated for subsequent studies in patients with AF. In the FIH study of MAA868, the half-life of MAA868 ranged from 20-28 days following s.c. administration. Furthermore, a sustained PD effect of >2-fold mean activated partial thromboplastin time [aPTT] prolongation was observed for ~30 days and returned to the baseline level by ~60 days post-dose after a single 150 mg s.c. dose administration in study X2101. These data support monthly administration of MAA868. Furthermore, assessment of the exposure-response relationship of MAA868 in healthy subjects demonstrated a nearly flat exposure-response for relevant PD parameters (aPTT, FXI coagulation activity and free FXI) at concentrations above 4 µg/mL which is consistent with the Day 29 total MAA868 concentrations achieved with the 150 mg single dose administration in healthy subjects (CMAA868X2101).

Given the half-life of MAA868 and the observed time to return to baseline aPTT levels, a prolonged washout/follow-up period of approximately 110 days from the last dose of MAA868 should be a sufficient monitoring period for patients.

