The study is comprised of 3 periods: screening period, treatment period, and follow-up period. The screening period may last up to 4 weeks. The treatment period is 91 days and consists of 3 monthly subcutaneous doses of MAA868 (or matching placebo). Study drug is administered at the study site on day 1 (visit 2), day 31 (visit 4), and day 61 (visit 6). During the treatment period, subjects will return to the study site on day 11, day 31, day 41, day 61, day 71, and day 91 for safety assessments. The follow-up period is 79 days and continues to day 170, allowing a 110-day washout period from the last study drug administration. During the follow-up period, subjects will return to the study site on day 101, day 121, and day 170 (EoS) for additional safety evaluations.

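### The protocol's on-treatment window for bleeding and thromboembolic events misdates the third dose and states no end for subjects who receive all three doses, and the SAP uses a longer window without declaring it

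*Protocol*

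**What the plan says.** Protocol 8.6 uses the same sentence in its bleeding paragraph and in its paragraph on the "composite safety endpoint of major cardiovascular, cerebrovascular, and venous thromboembolic events which occur on-treatment". Events count "from the first dose of the study drug to the last dose of the study drug + 30 days", and the sentence continues "if the subject permanently discontinues the study drug prior to the third dose on Day 91". Nothing else in 8.6 says when the window closes for a subject who does not stop early.

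Other places bear on the same window:

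- **Dosing days.** Under Protocol 3.1 the first dose is on Day 1, and the second and third are given "at the study center to patients on the Day 31 visit and Day 61 visit, respectively". Table 9 marks study drug on Days 1, 31 and 61 only, and SAP 2.2 gives the same days.
- **Bleeding endpoint.** Protocol 2.2: "Occurrence of confirmed major bleeding events, CRNM bleeding events and total bleeding events during the treatment period". SAP 3.2 also limits it to the treatment period, which the protocol synopsis sets at Day 1 to Day 91, 90 days.
- **Thromboembolic endpoint.** Protocol 2.3 gives no period, and neither does SAP 3.3.
- **SAP analysis.** Sections 7.8.8 and 7.8.10 summarise treatment-emergent adjudicated events and refer to section 7.7.2 for the definition. Section 7.7.2 is the secondary efficacy analysis. The definition is in 7.8.2 and runs from first dose to the end-of-study visit. Section 8 reports no departure from the protocol's planned analyses.

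**The concern.** A window rule for safety counts has to give every subject a start and an end. This one ties its only end to stopping before the third dose, so it is silent on subjects who take all three doses, who should be the majority. It also gives that dose a day on which the schedule shows none.

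The SAP would be the natural place to settle the matter, but it moves to a different and longer window, reaches it through a wrong cross-reference, and records no change. Whether an event between Day 91 and Day 170 counts towards the bleeding endpoint then depends on which document is followed. The protocol's endpoint excludes it; the SAP table includes it. Bleeding is a secondary safety endpoint, and Protocol 1.2 says the results will help select a phase 3 dose, so the table should be clear about the exposure period it describes.

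**Working it through.** **Can the plan's own day be reproduced?** The figure to check is Day 91 for the third dose.

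- Schedule: doses on Days 1, 31 and 61. With the ±2-day visit window in Table 9, the third falls on Days 59 to 63. The difference from the day written in 8.6 is 91 − 61 = 30 days.
- Cross-check: Protocol 3.2 describes "a prolonged washout/follow-up period of approximately 110 days from the last dose of MAA868". End of study is Day 170. From Day 61, 170 − 61 = 109 days, which agrees. From Day 91, 170 − 91 = 79 days, which does not.

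Day 91 as a dose day is therefore not reproduced.

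**Where does each rule end the window for a three-dose subject?** Length is end day minus Day 1.

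| Rule | End day | Length |
|---|---|---|
| Protocol 8.6 as worded | none stated | – |
| Last dose + 30 applied to everyone | 61 + 30 = 91 | 91 − 1 = 90 days |
| Treatment period (synopsis; Protocol 2.2 for bleeding) | 91 | 90 days |
| SAP treatment-emergent (7.8.2) | 170 | 170 − 1 = 169 days |

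The second and third rows agree, which is why Day 91 is taken as the protocol's evident intent. With the ±10-day window on the final visit, the SAP length is 159 to 179 days.

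**How far apart are protocol intent and SAP?**

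- Ratio: 169 / 90 = 1.88.
- Extra days: 169 − 90 = 79, the same 79 days that the synopsis assigns to follow-up (Day 91 to Day 170) and that Table 9 labels washout.
- Two cohorts with 12 MAA868 subjects each, all followed in full: 24 × 90 / 365.25 = 5.9 person-years against 24 × 169 / 365.25 = 11.1 person-years.

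**Early stoppers** do have an end under 8.6: 1 + 30 = Day 31 after one dose, and 31 + 30 = Day 61 after two.

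**The case against.** The strongest reply is that this is a drafting slip whose meaning can be recovered. For bleeding that largely stands: the treatment-period endpoint and last dose plus 30 days both give Day 91, so it would be too strong to say that bleeding has no usable window. For thromboembolic events there is no second source, and Day 91 has to be inferred from the intent of the sentence.

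A second reply is that the SAP gives every subject a definite window, so the tables can be programmed and nothing after Day 61 is lost. That is true, but the SAP window does not match the treatment-period endpoint in SAP 3.2, and the pointer leads to a section without the definition. The protocol version on which the SAP is based (Version 2.0) carries the same 8.6 sentence, so a later protocol change does not explain the difference.

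A third reply is that last dose plus 30 days also gives unequal follow-up: 30, 60 or 90 days after one, two or three doses. This stands, and is a reason to keep the count to end of study beside it.

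A reader might go further and infer that, taken literally, a three-dose subject's window closes at the third dose on Day 61, losing the last 30 days of treatment. That requires the condition to govern only the added 30 days. The sentence reads at least as naturally with the condition governing the whole end rule, in which case no end is stated. No other passage supports closing at Day 61, and the SAP does not do so. Multipliers built on a 60-day window should not be used.

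**Conclusion.** Protocol 8.6 is wrong as written: the day given for the third dose conflicts with 3.1, Table 9 and the SAP, and no end is stated for three-dose subjects. The SAP does not cure this, because it adopts an undeclared window to end of study that differs from the treatment-period bleeding endpoint.

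The size is 90 against 169 days per three-dose subject, a factor of 1.88. This assumes doses and visits on their nominal days, full follow-up, and Day 91 as the protocol's intended end. It is a ratio of follow-up time. A reader might infer 1.88 times as many events, but that needs a constant event rate through washout, which the documents do not support: Protocol 3.2 reports a half-life of 20 to 28 days and aPTT back at baseline by about 60 days after a single 150 mg dose.

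This should be fixed, but it does not threaten the trial's main result. The counts are secondary (bleeding) and exploratory (thromboembolic), up to 48 subjects are planned, and no significance tests are planned. SAP 7.8.8 and 7.8.10 list all adjudicated events, so either window can be recounted.

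**What to change.** 1. In both paragraphs of Protocol 8.6, give one analysis window for every subject: first dose to actual last dose plus 30 days, which is Day 91 when the third dose falls on Day 61. Delete "if the subject permanently discontinues the study drug prior to the third dose on Day 91".
2. In SAP 7.8.8 and 7.8.10, tabulate that window beside the count to end of study, with each labelled.
3. Correct the pointer in both SAP sections from 7.7.2 to 7.8.2.
4. State how the window treats interrupted or restarted dosing, which Protocol 5.6 allows: which first dose opens it, and whether time off drug counts.
5. Record the difference from the protocol in SAP section 8.

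The cost is one sentence in two protocol paragraphs, one SAP derivation with an added set of counts in two tables, and a few lines of text. No new data are needed. The change concerns the analysis window only and proposes nothing about the dosing schedule.
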